2 STUDY SCHEMA

3 PROTOCOL SYNOPSIS

STUDY OBJECTIVES: The primary objective of this study is to assess the efficacy of bupropion in reducing methamphetamine use in subjects with methamphetamine dependence who report using methamphetamine 29 or less days during the 30 days prior to signing consent. It is hypothesized that bupropion, compared to placebo, will be associated with an increase in the proportion of subjects who achieve abstinence (confirmed by at least two methamphetaminenegative urines and no methamphetamine-positive urines) each week during the last two weeks (Weeks 11 and 12) for non-daily users. Secondary objectives include but are not limited to: assessing the success or failure to achieve abstinence (confirmed by at least two methamphetamine-negative urines and no methamphetamine-positive urines) each week during the last two weeks (Weeks 11 and 12) for subjects using methamphetamine 18 or less days during the 30 days prior to signing consent, assessing the safety of bupropion in this study population, assessing other measures of efficacy of bupropion in reducing methamphetamine use or craving, and other psychological assessments of methamphetamine dependence. In addition, if efficacy findings are promising, preliminary evaluations of the genetic markers associated with a positive clinical outcome or predictive of bupropion safety and efficacy including associations with bupropion pharmacokinetics (PK) may be performed.

STUDY DESIGN: This is a double-blind, placebo-controlled, parallel-group design study in which, after an up to 4-week screening period which includes a 2-week baseline assessment period, 200 subjects will be randomly assigned in an approximately 1:1 ratio to either receive placebo or bupropion (100 subjects per group) daily for 12 weeks, with follow-up assessments weekly for 4 weeks after completion of study interventions. Adaptive randomization will be used to balance study intervention groups within each clinical site, based on methamphetamine use (18 or less days *versus* 19-29 days out of 30 days prior to signing consent), severity of depression symptoms [Hamilton Depression Rating Scale (HAM-D) score ≤ 12 *versus* >12], and presence of adult Attention Deficit/Hyperactivity Disorder (Adult ADHD Clinical Diagnostic Scale - ACDS).

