- Y. Proportion of subjects who met the criteria for being abstinent according to the primary outcome measure during Weeks 11 and 12 who continue to be abstinent Weeks 13 through 16 as determined by self-report and confirmation by methamphetamine negative urine sample.
- **Z.** Proportion of subjects who met the criteria for being abstinent according to the primary outcome measure who continue to be abstinent Weeks 13 through 16 as determined by self-report alone.

The proportions will be calculated using the number of subjects who meet the criteria for continued abstinence as described above by the number who were abstinent during weeks 11 and 12 as defined by the primary outcome measure.

Plasma Levels of Bupropion and BDNF

Bupropion is primarily metabolized in human liver by CYP 2B6, an isoform that shows high interindividual variability in expression and catalysis which has been hypothesized to account for the variability in treatment response and toxicity associated with bupropion. Rapid clearance of bupropion via hydroxylation could account for treatment failure, likewise, slow clearance could account for toxicity. Recently, the 6B haplotype of CYP 2B6 has been shown to be a significant predictor of bupropion hydroxylation in human liver microsomal preparations, thus suggesting that individuals with this haplotype may be poorer responders to treatment. At steady state, the mean C_{max} following a 150-mg dose of bupropion every 12 hours is 136 ng/mL. Bupropion plasma levels will be examined for correlation to CYP 2B6 haplotypes and to treatment success.

Elevated plasma BDNF levels are associated with methamphetamine neurotoxicity, and are known to decline during abstinence from methamphetamine. Since bupropion also has an independent effect on BDNF, plasma samples will be tested for bupropion level at the same timepoints as plasma for BDNF is obtained. This will allow the evaluation of whether BDNF is affected differently in subjects receiving bupropion compared to those receiving placebo, and whether this effect influences methamphetamine use or abstinence. In addition, it is also hypothesized that methamphetamine users who have the BDNF 66Val homozygote will be more likely to benefit from bupropion than those who do not.

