15.4 Analysis Plan

15.4.1 Efficacy Assessments

Each of the primary and secondary efficacy outcome measures listed in sections 15.2.1 and 15.2.2 will be analyzed for the ITT population. The primary outcome measure also will be analyzed and for the "evaluable" and "expanded evaluable" populations. Each of these analyses will be conducted in two ways: 1) comparing the bupropion and placebo groups independent of

compliance data and 2) comparing the medication-compliant subjects in the bupropion group with both the placebo group and the subjects who were not medication-compliant in the bupropion group. Medication-compliant subjects are defined as individuals testing positive for bupropion or its major metabolite in at least 50% of urine samples (in aggregate) obtained during weeks 1 through 10 and at least 66% of urine samples (in aggregate) obtained during weeks 11 and 12. Finally, the analyses described in section 15.2.3 will be conducted for the ITT population.

While there is every intent to be complete in describing the analyses to be performed, it is not possible to anticipate every contingency and some adjustments may be required to meet constraints posed by the structure of the data.

Statistical tests will be two-sided at a 5% Type I error rate. Confidence intervals will be two-sided with a 95% confidence coefficient.

Primary Efficacy Outcome Measure

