15.5 Sample Size calculation

Sample size estimates were performed using the last two week's abstinence rates from a prior Phase 2 trial examining the efficacy of bupropion for the treatment of methamphetamine dependence. The proportion of successful participants was 0.238 and 0.057 for the bupropion and placebo arms, respectively. The proportion of participants achieving a successful outcome was compared between arms using a two-tailed Fisher's exact test (p = 0.01). For a power of 95% and a Type I error rate of 5%, a sample size of 100 per group (total of 200 subjects) is required.

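### Relapse outcomes Y and Z are tested between arms only among Week 11-12 abstainers, so the test is not a randomised comparison and has little power

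*Protocol*

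**What the plan says.** Section 15.2.2, under its relapse-prevention subheading, defines Y as the "Proportion of subjects who met the criteria for being abstinent according to the primary outcome measure during Weeks 11 and 12" who are still abstinent in Weeks 13 to 16 by self-report with a negative urine. Z is the same by self-report alone. The sentence after Z fixes the arithmetic for both: the number who continue is divided "by the number who were abstinent during weeks 11 and 12 as defined by the primary outcome measure". The efficacy paragraph of the synopsis gives the same conditional definition.

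Section 15.4.1 introduces its table of methods as between-group comparisons of the secondary outcomes and puts Y and Z in the Chi-square or Fisher row. It also states: "Statistical tests will be two-sided at a 5% Type I error rate". Neither outcome is marked as descriptive, although section 15.4.2 does mark the adverse-event comparison that way.

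The other listed methamphetamine-use outcomes, and the non-binary success score in section 15.2.3, stop at Week 12 or earlier. No outcome in section 15.2 compares abstinence through Week 16 over all ITT subjects.

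**The concern.** Being abstinent in Weeks 11 and 12 is the primary endpoint, and the trial's hypothesis is that bupropion changes who reaches it. Restricting a comparison to those who reach it selects subjects on a result of treatment. The bupropion and placebo abstainers are then not the groups that randomisation made comparable, and a p-value comparing them does not test an effect of the drug on staying abstinent.

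Two practical consequences follow. The subset is small and lopsided if the planning rates hold. The direction of Y or Z can also differ from the direction of lasting abstinence in the randomised groups. Secondary objective 5 in section 5.2 concerns abstinence four weeks after dosing ends, and Y and Z are the only listed outcomes that use abstinence in Weeks 13-16. As planned, its only between-arm test is this one.

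**Working it through.** **Inputs from the Protocol.** Section 15.5: "The proportion of successful participants was 0.238 and 0.057 for the bupropion and placebo arms, respectively"; "a sample size of 100 per group (total of 200 subjects) is required"; 95% power at 5% type I error; two-tailed Fisher test named beside the rates. Section 15.4.1: two-sided 5% tests. Synopsis: subjects "randomly assigned in an approximately 1:1 ratio".

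**The plan's own figure.** Exact power of the two-sided Fisher test for 0.238 versus 0.057 is 0.951 at 100 per arm and 0.948 at 99. The stated 100 per group is reproduced, so these rates can be used for projection.

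**Size of the Y/Z denominators.** Expected abstainers = n × p:
- bupropion 100 × 0.238 = 23.8, about 24 (95% binomial range 16 to 32);
- placebo 100 × 0.057 = 5.7, about 6 (95% binomial range 2 to 11).

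With 6 placebo subjects, the two expected counts in the placebo row sum to 6, so at least one is 3 or less. By the usual expected-count convention the Fisher test would apply.

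**Power of the planned test, 24 versus 6.** The Protocol gives no retention rates for Weeks 13-16, so those below are assumptions shown over a range.

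| Continuing, bupropion vs placebo | Exact Fisher power |
|---|---|
| 50% vs 50% | 2.1% (false positives) |
| 70% vs 50% | 12.6% |
| 80% vs 50% | 29.2% |
| 90% vs 50% | 53.2% |
| 50% vs 70% | 6.1% |
| 100% vs 70% | 58.0% |

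Against 50% on placebo, 80% power needs about 99% continuing on bupropion.

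**Direction, by example counts.**
- 14 and 4 still abstinent: Y = 14/24 = 58% versus 4/6 = 67% (Fisher p = 1.00). Over all randomised: 14/100 versus 4/100 (Fisher p = 0.024, Chi-square p = 0.013).
- 12 and 4: Y = 50% versus 67% (Fisher p = 0.66). Over all randomised: 12% versus 4% (Fisher p = 0.065, Chi-square p = 0.037).
- 12 and 3: Y = 50% versus 50%. Over all randomised: 12% versus 3% (Fisher p = 0.029).

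**When a reversal arises.** Assume the 5.7% who abstain on placebo would also abstain on bupropion and that 75% of them continue on either arm. The extra 0.238 − 0.057 = 0.181 abstain only on bupropion, and a fraction r of them continue. Then

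Y on bupropion = (0.057 × 0.75 + 0.181 × r) / 0.238; abstinent through Week 16 over all randomised = 0.057 × 0.75 + 0.181 × r. Placebo has Y = 75% and 0.057 × 0.75 = 4.3% over all randomised.

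| r | Y, bupropion (placebo 75%) | All randomised, bupropion (placebo 4.3%) |
|---|---|---|
| 0.2 | 33% | 7.9% |
| 0.4 | 48% | 11.5% |
| 0.6 | 64% | 15.1% |
| 0.75 | 75% | 17.9% |

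Below r = 0.75, Y favours placebo although bupropion has more lasting abstainers. At r = 0.75 the arms are equal on Y, and above it there is no reversal.

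**Power of the all-randomised comparison, 100 versus 100.** With 50% and 70% continuing, the rates are 0.238 × 0.5 = 11.9% and 0.057 × 0.7 = 4.0%, with 46% power. With 50% continuing in both arms they are 11.9% and 0.057 × 0.5 = 2.9%, with 63% power.

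**The case against.** Only a person who has stopped can relapse, so conditioning on abstinence is natural for a relapse outcome. Objective 5 asks for rates of continued abstinence and, unlike objective 4, does not mention comparison with placebo. A reader might infer that Y and Z cannot answer objective 5 at all. The documents do not support that: the conditional rate describes continued abstinence among abstainers, as the objective is worded. What it cannot carry is the between-arm test that section 15.4.1 adds.

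A reader might also infer that Y will point the wrong way, or that bupropion abstainers are more marginal. Neither follows from the Protocol. It gives no retention rates, and extra abstainers need not relapse more often. Even with 50% versus 70% continuing, the planned test is non-significant about 94% of the time, so the reversal would be a numerical direction resting on about six placebo subjects.

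The all-ITT outcome is not a corrected measure of relapse. When both arms continue at 50%, a test that finds nothing is right about relapse; the 63% power of the all-ITT version comes entirely from the Week 11-12 difference that the primary outcome already tests. That limitation stands, and the outcome must be labelled accordingly.

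The statement in section 15.4.1 that all secondary outcomes are analysed in the ITT population might be read as a contradiction. It is a weak one, because a restricted outcome can be computed within the ITT set. Outcome A is also restricted, but by a baseline variable, which leaves randomisation intact; Y and Z are not.

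Finally, the denominator is stated openly, a reader could multiply Y by the primary success rate, and no secondary hypothesis in section 15.1 concerns Weeks 13-16. This lowers the stakes. It does not make the planned test a randomised comparison.

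**Conclusion.** The point holds for the between-arm test of Y and Z. The loss of the randomised comparison follows from the definitions alone and needs no assumption about retention. The subset size of about 24 versus 6 is a projection from the planning rates, not a figure the Protocol states. At that size power is roughly 13% to 53% for 70% to 90% versus 50% continuing.

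A reversal against bupropion is possible, not established. It depends on the assumption that subjects who abstain only because of the drug relapse more often. The effect is confined to Y, Z and the between-arm reading of objective 5. The primary analysis and the sample size are untouched. The change should be made, but it is not critical to the trial.

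**What to change.** In sections 15.2.2 and 15.4.1, for the between-arm test, use the proportion of all ITT subjects who meet the primary success criterion and remain abstinent through Weeks 13-16. Define it in both the urine-confirmed and the self-report version. Count subjects who miss the primary criterion, and those with missing follow-up, as failures; this extends the failure rule that section 15.2.1 already applies. Label it sustained abstinence (achieving it and keeping it).

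Keep the current Y and Z, reported by arm with their numerators and denominators, as descriptive and without a test. Remove them from the Chi-square or Fisher row and put the new outcome there.

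The cost is a sentence or two of text and no new data, since sections 12.7 and 13.5 already schedule weekly urine and self-report in Weeks 13-16. The drawback is that the new outcome is correlated with the primary and can differ between arms with no difference in relapse; the descriptive Y and Z beside it let a reader see which is the case.

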15.2.3 Additional Secondary Outcome Measures and Analyses

The following additional analyses will be conducted:

i. A novel, non-binary method for evaluating success and failure (McCann and Li, submitted to CNS Neuroscience & Therapeutics) will be used to test the hypothesis that bupropion, as compared to placebo, will increase abstinence from methamphetamine that lasts for multiple weeks and through the end of the 12-week treatment phase. A subject will be regarded as abstinent from methamphetamine during a given week if at least two methamphetamine-negative urines and no methamphetamine-positive urines are provided, and a subject who achieves abstinence during Weeks 11 and 12 will be regarded as a success. A subject who drops out of

the study, provides one or more methamphetamine-positive urines during Weeks 11 and 12, or provides less than two urines per week during Weeks 11 and 12 will be regarded as a failure. For successful subjects, urine results from all weeks prior to Week 11 will be evaluated and, again, they will be regarded as abstinent from methamphetamine during those weeks with at least two methamphetamine-negative urines and no methamphetamine-positive urines. Their degree of success will then be calculated by determining the "Number of Beyond-Threshold Weeks of Success" (NOBWOS), with the threshold set at 1 week of end-of-study abstinence. For example, a subject achieving 8 weeks of end-of-study abstinence (abstinence on weeks 5 through 12) will be assigned a NOBWOS value of 7. Similarly, a subject who achieves the minimum level of success (abstinence on weeks 11 and 12) will be assigned a NOBWOS value of 1. Treatment failures will be assigned a NOBWOS value of 0. NOBWOS values will then be compared between groups using a two-sided Van der Waerden two-sample test.

ii. The relationship between self-reported baseline level of methamphetamine use (number of days reported use during the 30 days immediately prior to screening) and the percentage of urines positive for bupropion and/or its major metabolite throughout the 12-week treatment period for all subjects randomized to the bupropion group will be evaluated using a logistic regression analysis. The percentage of urines testing positive for bupropion and/or its metabolite will serve as the dependent variable and the number of days reported use prior to screening will serve as the independent variable.

iii. The relationship between the percentage of methamphetamine-positive urines during screening and the percentage of urines positive for bupropion and/or its major metabolite throughout the 12-week treatment period for all subjects randomized to the bupropion group will be evaluated using a logistic regression analysis. The percentage of urines testing positive for bupropion and/or its metabolite will serve as the dependent variable and the percentage of urines testing positive for urines testing positive for methamphetamine during screening will serve as the independent variable.

15.3 "Intention-to-Treat," "Evaluable," and "Expanded Evaluable" Subject Populations

The ITT population is defined as subjects who were randomized and received at least 1 dose of investigational product. The evaluable population is defined as the subjects who are eligible to participate in the study in accordance with the inclusion and exclusion criteria and who received at least 4-weeks of investigational product, and provided at least 2 urine samples per week that were analyzed for methamphetamine during the last two weeks of the study (Weeks 11 and 12). The expanded evaluable population is defined as the subjects who are eligible to participate in the study and who received at least 4-weeks of investigational product, and provided at least 2 urine samples per week that were analyzed for methamphetamine during the study and who received at least 4-weeks of investigational product, and provided at least 2 urine samples per week that were analyzed for methamphetamine during their last 2 weeks of participation in the trial (dropouts allowed).

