8 STUDY DESIGN

This is a double-blind, placebo-controlled, parallel-group design study in which, after screening and a 2-week baseline period, 200 participants will be randomly assigned to either receive placebo or bupropion (100 subjects per group) daily for 12 weeks, with a follow-up assessment 4 weeks after completion of study interventions. Adaptive randomization will be used to balance study intervention groups based on site, methamphetamine use (18 or less *versus* 19-29 days out of 30 days prior to signing consent), severity of depression symptoms (HAM-D score ≤ 12 *versus* >12), and presence of Adult ADHD.

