13.3 ASSESSMENTS DURING THE INTERVENTION PHASE

Over the 12-week period of study interventions, subjects will return to the clinic three times per week (ideally on Monday, Wednesday, and Friday). Assessments will be performed as follows:

On Day 1, Week 1 before dosing:

All women will have a pregnancy test on the day that first dose of investigational product is administered prior to the dose to confirm that the subject is not pregnant.

At each visit:

- 1. SUR
- 2. Urine methamphetamine and creatinine
- 3. Alcohol breathalyzer (if necessary, according to institutional policies)
- 4. AEs
- 5. Concomitant medications
- 6. Compliance with study interventions [investigational product dosing (by subject self report; pill counts are performed once per week) and CBT]

Once per week preferably at the first visit of each week (except at the end of Week 12):

- 1. Urine drug screen (urine specimen sent to central laboratory for analysis)
- 2. BSCS
- 3. CGI-S
- 4. CGI-O
- 5. Vital signs
- 6. Compliance with study interventions (pill count)

At Weeks 6 and 12, preferably at the first visit of the week:

- 1. Blood for RNA analysis
- 2. Blood for trough plasma bupropion levels (hold morning dose until blood sample obtained)
- 3. Blood for plasma BDNF levels

At Weeks 4 and 8, preferably at the first visit of the week, and Week 12 at the last visit of the week:

- 1. Pregnancy test
- 2. AISRS

At Weeks 2, 4, 6, 8, 10 and 12, preferably at the first visit of the week (except at the end of Week 12):

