Following randomization, during the investigational product dosing period of the study and at each of the follow-up visits, urine will be collected 3 times per week (generally Monday, Wednesday, and Friday, barring holidays and schedule conflicts) and sent to a central laboratory. The central laboratory will: a) perform qualitative analysis for the 1st sample collected each week for cocaine, methamphetamine/amphetamines, tetrahydrocannabinol, opiates, and benzodiazepines, b) screen all samples for amphetamines/methamphetamine, creatinine, and c) will quantitate amphetamines and methamphetamine for all samples, qualitatively screened positive for methamphetamine/amphetamines.

All specimens collected and screened positive by the central laboratory for methamphetamine/amphetamines will be subjected to methamphetamine quantitative analysis performed at central laboratory. The back-up sample retained at the site will be stored frozen until the NIDA data coordinating center has notified the site that it can be disposed.

Urine Toxicology Screen Using an Onsite Testing Device. During the screening/baseline period, urine will be collected 3 times per week (generally Monday, Wednesday, and Friday, barring holidays and schedule conflicts). After the backup aliquot and the central laboratory testing aliquot have been obtained, the sample will be analyzed using an on-site testing device (tetrahydrocannabinol, methamphetamine, cocaine, amphetamines, barbiturates, opiates and benzodiazepines). Samples positive for amphetamine/methamphetamine (the on-site testing device has a cutoff of greater than or equal to 500 ng/mL) will be considered as positive for methamphetamine for inclusion criteria purposes.

Medical Urinalysis. Urine will be collected and analyzed for color, appearance, specific gravity, pH, blood, protein, glucose, ketones, leukocytes, bilirubin and nitrites. Analysis will be conducted at a local laboratory.

Urine Pregnancy Test. An on-site qualitative urine pregnancy test that evaluates human β -chorionic gonadotropin will be used.

Bupropion and Metabolite (hydroxybupropion) Assays. Urine samples collected during the treatment period for the bupropion group will be assayed by a central lab for bupropion and its

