15.2.1 Primary Outcome Measure

The primary efficacy outcome measure is a binary measurement of treatment success or failure, where a subject who successfully achieves two weeks of abstinence during the last two weeks of the investigational product dosing period (Weeks 11 and 12) is scored as a success. During the investigational product dosing period, each subject is asked to provide three urine samples per week. A successful outcome requires (1) all urine samples in the last two weeks are negative for methamphetamine (< 300 ng/mL quantitative result of negative qualitative result) and (2) a minimum of two urines samples collected and tested per each of the last two weeks during investigational product dosing. A subject who drops out before the last 2 weeks of the treatment period is scored as a failure in the analysis. A subject who stays on study to the beginning of Week 11 but who does not provide at least 2 urine samples per week during Weeks 11 and 12 is scored as a failure.

15.2.2 Secondary Outcomes Measures Effect on methamphetamine and other drug use during Study Weeks 1-12 (except J)

- A. The secondary efficacy outcome measure is also a binary measurement of treatment success or failure, where a subject who successfully achieves two weeks of abstinence during the last two weeks of the investigational product dosing period (Weeks 11 and 12) is scored as a success. The study population for this outcome measure is defined as those subjects with methamphetamine dependence who report using methamphetamine 18 or less days during the 30 days prior to signing consent.
- B. Methamphetamine non-use weeks during study Weeks 1 through 12. Use weeks are defined as each 7-day period staring with the first day of investigational product administration. A non-use week is any week in which all of the urine drug screens for methamphetamine were negative (< 300 ng/mL). Conversely, a use week is any week in which at least one of the urine drug screens for methamphetamine was positive (≥ 300 ng/mL). If no drug screening results are available, the data for that week is considered as missing.

- **C.** Log₁₀ weekly mean quantitative urine methamphetamine level.
- **D.** The proportion of successful subjects with different patterns in the reduction in drug use examined as follows:

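### Analyses ii and iii apply logistic regression to a per-subject percentage of drug-positive urines with no variance for within-subject correlation, so neither default fit holds the 5% level.

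*Protocol*

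**What the plan says.** Protocol section 15.2.3 adds two analyses confined to the bupropion arm. In each, the relationship "will be evaluated using a logistic regression analysis". For item ii: "The percentage of urines testing positive for bupropion and/or its metabolite will serve as the dependent variable and the number of days reported use" before screening is the independent variable. Item iii concerns "The relationship between the percentage of methamphetamine-positive urines during screening and the percentage of urines positive for bupropion and/or its major metabolite", and its outcome is the same: "The percentage of urines testing positive for bupropion and/or its metabolite will serve as the dependent variable and the percentage of urines" positive for methamphetamine at screening is the predictor.

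The number of urines behind each percentage follows from the visit schedule. Section 15.2.1 states that "each subject is asked to provide three urine samples per week", and section 13.3 that "Over the 12-week period of study interventions, subjects will return to the clinic three times per week". Section 13.6.29 has the treatment-period urines of the bupropion group assayed centrally for drug and metabolite. Section 8 plans 100 subjects in that group.

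Section 15.4.1 assigns the section 15.2.3 analyses to the ITT population, sets tests at two-sided 5%, and allows unspecified adjustments for the structure of the data. Section 16.3 says the analysis will follow the protocol's own analytical plan.

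**The concern.** Ordinary logistic regression takes a binary response or a count of events out of trials. A percentage is neither, so an analyst must decide how to enter it. The two obvious choices are positives out of urines collected, or one fraction per subject. Each carries a built-in variance assumption, and the protocol replaces neither with an overdispersion term, clustering or a robust variance.

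Independence of urines within a subject is hard to defend on the protocol's own facts. Sections 15.1 and 15.4.1 classify whole subjects as medication-compliant or not, which treats adherence as a property of the person. The pharmacology also links neighbouring samples. Section 4.2.3 gives a mean steady-state bupropion peak of 136 ng/mL, hydroxybupropion peaks about 10 times higher, and a metabolite half-life of about 20 hours. Section 13.6.29 calls a urine positive at 5 ng/mL. As an illustration from plasma figures (urine levels will differ), 1,360/5 = 272, which is log2(272) ≈ 8.1 half-lives, or about 162 hours (6.7 days). With visits every two to three days, one dosing episode could make several consecutive urines positive.

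The protocol treats comparable data differently elsewhere. The section 15.4.1 table gives GEE to the weekly proportion of negative urines for other drugs (outcome I), and a t-test or nonparametric test, with the subject as unit, to the overall proportion of methamphetamine-negative urines (outcome G).

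At stake is whether the reported association between baseline use and medication-taking has a valid p-value and interval.

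**Working it through.** **Plan's own figure.** The protocol gives no number for analyses ii and iii. The arm size they use comes from section 15.5 (0.238 versus 0.057, 95% power, two-sided 5%, 100 per group). That reproduces: exact enumeration of Fisher's test at 100 per arm gives power 0.951.

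**Inputs from the protocol.** Three urines per week × 12 weeks gives m = 36 at most; about 100 subjects; two-sided α = 0.05.

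**Assumed inputs.** Within-subject correlation ρ, shown from 0.05 to 0.8; mean positivity 60% in the simulations. The protocol gives neither.

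**Formulae.** Let p be the probability that a urine is positive. The variance of one subject's proportion is p(1 − p)/m × [1 + (m − 1)ρ].

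- Unadjusted events/trials assumes p(1 − p)/m. True SE / model SE = sqrt(1 + (m − 1)ρ).
- One fractional record per subject with model-based errors assumes p(1 − p). True SE / model SE = sqrt([1 + (m − 1)ρ]/m).

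The first ratio equals 1 only at ρ = 0 and the second only at ρ = 1. Neither default is right in between.

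**Results at m = 36.** Ratios are from the formulae. Type I error is from beta-binomial simulation with a null slope and 100 subjects (600 to 1,000 replicates), except where marked.

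| ρ | Events/trials: SE ratio | Type I error | One record: SE ratio | Type I error |
|---|---|---|---|---|
| 0.05 | 1.66 | 24% by formula, 23% simulated | 0.28 | 0% |
| 0.1 | 2.12 | 37% | 0.35 | 0% |
| 0.3 | 3.39 | 57–59% | 0.57 | 0.2% |
| 0.6 | 4.69 | 66–67% | 0.78 | 0.5% |
| 0.7 | 5.05 | not simulated | 0.84 | not simulated |
| 0.8 | 5.39 | 70% | 0.90 | 1.2% |

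The 24% by formula is 2 × [1 − Φ(1.96/1.66)]. Simulated SE ratios agree with the formulae: for events/trials, 2.1–2.2 at ρ = 0.1 and 3.4–3.6 at 0.3; for one record, 0.36 and 0.56.

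**Fewer urines.** Over ρ = 0.05 to 0.7 the events/trials ratio runs from 1.47 to 4.14 with m = 24 and from 1.36 to 3.59 with m = 18. When about 40% of simulated subjects provide only part of their urines, type I error is 34%, 53% and 68% at ρ = 0.1, 0.3 and 0.6.

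**After correction.** Events/trials with a Pearson overdispersion scale gives type I error of 5–7% for ρ = 0.1 to 0.6. A fractional logit with robust errors gives 4–6% for ρ = 0.05 to 0.8 with all 36 urines, and 4–7% with simulated dropout.

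**The case against.** A reader might infer that the plan treats 36 correlated urines as independent and so understates standard errors by a set factor, say two- to fourfold. The text does not support that. It defines one percentage per subject and never says that the single urine is the unit. If the percentage is entered as one record, the error reverses. The nearest analogue, outcome G, is analysed by subject, which points away from the events/trials reading. A two- to fourfold figure would also need ρ between about 0.09 and 0.43 with all 36 urines, and the protocol states no correlation. All of this stands, so the size must be conditional.

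A reader might also infer that a false positive would be used to explain efficacy by frequency of use. Section 15.2.3 says only that the relationship will be evaluated. The case for limiting benefit to low-frequency users in section 4.2.2 is pharmacological, and no hypothesis in section 15.1 depends on these analyses. The type I error rates are also two-sided: under the null, about half of the rejections would point to heavier users taking more medication, not less.

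Finally, dispersion scales and robust variances are commonly SAP detail, and section 15.4.1 permits adjustments. This stands only in part. The protocol itself chose both the model and the outcome, section 16.3 makes its analytical plan the governing text, and the allowance for adjustments names no remedy.

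**Conclusion.** The point holds in conditional form. The named method does not fit the named outcome, and both default ways of fitting it miss the two-sided 5% level, in opposite directions. Unadjusted events/trials is anti-conservative by about 1.7- to 5.0-fold in the standard error. This rests on m = 36 and an assumed ρ of 0.05 to 0.7, and shrinks with fewer urines. One fractional record per subject with model-based errors is conservative, with type I error about 1% or less in the simulations and a matching loss of power. The protocol does not settle which would apply, so neither direction nor size can be stated as fact. The consequence is confined to two additional secondary analyses within the bupropion arm; the primary comparison and its sample size are untouched.

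**What to change.** In section 15.2.3, items ii and iii, name one model with the subject as the independent unit. Any of these would serve:

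- logistic regression on positives out of urines collected, with an overdispersion scale (quasi-binomial);
- the same model with subject-clustered robust standard errors;
- a fractional logit on each subject's percentage with robust standard errors.

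Report the slope with its 95% CI. The choice should be fixed in advance because the options are not interchangeable: when urine counts differ through dropout or missed visits, events/trials weights subjects by the number of urines, whereas the fractional logit weights them equally.

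The cost is one line of wording and a small change in code, with no new data. Compared with an unadjusted events/trials fit, the intervals will be wider; compared with a one-record model-based fit, they will be narrower.
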